6.3 PATIENT SETS ANALYSED

Only one analysis population (Treated Set) will be considered for efficacy and safety (except ECG).

The Treated Set consists of all patients who received at least one application of the BI drug BI 6727.

Trial medication is defined as BI 6727.

First administration of trial medication is defined as date of first administration of BI 6727.

ECG

Per protocol set (PPS):

This is a subset of the Treated Set, restricted to patients, who have an ECG assessment in both courses (e.g. patients, who were replaced will be excluded).

[REDACTED]

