### **3. DESCRIPTION OF DESIGN AND TRIAL POPULATION**

#### **3.1 OVERALL TRIAL DESIGN AND PLAN - DESCRIPTION**

Due to the methodology of this trial (dose escalation), it is not possible to predict the number of patients necessary to reach the objectives. An estimated total of up to 80 patients might be necessary to establish MTD. A total of 24 patients will be treated at MTD. Actual accrual will depend on the number of dose levels tested and the adverse events observed. Patients non evaluable with respect to MTD will be replaced. Patients with a histologically or cytologically confirmed diagnosis of a malignant solid tumour refractory or not amenable to standard therapies are eligible for this trial. It is planned to have the trial performed at one centre, depending on enrolment more centres may be initiated.

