#### **4.1.6 Selection and timing of doses for each subject**

BI 6727 will be administered as a short infusion over 60 minutes using an infusion pump, on day 1 of each course (the start and end time of the infusion needs to be documented in the e-CRF). Immediately following the infusion of BI 6727 the infusion tubing will be washed with 100 mL physiological sodium chloride (0.9% NaCl) solution for a maximum duration of 10 minutes (The end time of the washing step needs to be documented in the e-CRF). BI 6727 should be administered strictly intravenously.

Initially, three patients will be treated per dose level. When at the ongoing dose level one patient experiences drug-related dose limiting toxicity (DLT; for definition, please refer to section 5.2.1) the number of patients treated at that dose level will be increased to a maximum of six evaluable patients. When no further patient experiences DLT the dose will be escalated to the next level. When two or more patients experience DLT in any dose cohort, other than the

expansion cohort at MTD level, enrolment into this dose cohort will be stopped. In order to define the maximum tolerated dose (MTD) three additional patients will be treated at one dose tier below unless six have already been treated at that dose tier. The MTD (see also section 5.2.1) is the highest dose at which not more than one patient out of six experiences DLT (R01-0028). Should safety data of patients treated at the next lower dose indicate a sufficient safety margin another escalation to an intermediate dose can be chosen after discussion between the investigator and the clinical monitor.

Once the MTD is determined patient enrolment at higher dose tiers will be suspended. Further patients will be included at the MTD level until a total of 24 patients will have been treated at the MTD.

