### **6.3.1 Replacement of patients**

Patients withdrawn or patients who miss more than one visit during their first treatment course will be replaced. Patients who miss one visit may be replaced after discussion between the sponsor and the investigator.

Patients who withdraw due to DLT will not be replaced.

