## 7.3 PLANNED ANALYSES

Only one analysis population (the treated set) will be considered for efficacy and safety analyses. No Per protocol population will be used for analyses, however protocol violations will be described.

**Treated Set** consists of all patients who received at least one application of BI 6727

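### The first-course DLT limit that defines the MTD is 17% in the protocol but 33% in the SAP, and the visible text does not fix the denominator

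*SAP*

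**What the plan says.** **Limit.** Protocol 5.2.1 defines the MTD by a first-course DLT incidence of no more than 17%, which it equates with 1/6. Protocol 5.2.1 and 7.3.1 also place the MTD one step below the dose at which two or more of at most six patients had a DLT. SAP 5.1 defines it by a first-course incidence of at most 33% in a single dose cohort. SAP 3.2 still describes a 3+3 design.

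**Counting basis.** Protocol 3.1: "Patients non evaluable with respect to MTD will be replaced". Under protocol 4.1.6, after one DLT "the number of patients treated at that dose level will be increased to a maximum of six evaluable patients". Protocol 7.3.1 repeats that non-evaluable patients are replaced. Protocol 6.3.1 adds: "Patients withdrawn or patients who miss more than one visit during their first treatment course will be replaced". It makes one exception: "Patients who withdraw due to DLT will not be replaced". Protocol 5.2.1 also replaces patients whose treatable adverse events were not treated adequately.

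**Analysis population.** Protocol 7.3: "Only one analysis population (the treated set) will be considered for efficacy and safety analyses". SAP 6.3: "Only one analysis population (Treated Set) will be considered for efficacy and safety (except ECG". The Treated Set is everyone dosed at least once. For the ECG per protocol set, SAP 6.3 notes that "patients, who were replaced will be excluded". No visible sentence says the same, or the opposite, for DLT. The visible part of SAP 7.7.1.1 promises the number of patients with a course-1 DLT by initial treatment and names no denominator.

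**The concern.** DLT in course 1 is the primary endpoint, and SAP 5.1 expresses the MTD as an incidence. An incidence needs a limit and a denominator. The two documents give different limits, and the visible text allows two denominators: the patients the escalation rule counted, or everyone dosed. The same data could then appear to confirm the declared MTD under one combination and contradict it under another.

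A narrower gap concerns a DLT in a patient who is replaced for a reason other than withdrawal due to DLT. One example is a patient who stays on trial but misses more than one course-1 visit. The stopping rule in protocol 4.1.6 begins "When two or more patients experience DLT in any dose cohort" and does not restrict this to evaluable patients. Its letter suggests that such a DLT counts, but no visible text confirms it.

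**Working it through.** **Step 1. The protocol's own figure.** Protocol Table 7.6: 1 gives the chance of two or more DLTs in six patients: P = 1 − (1−p)^6 − 6p(1−p)^5.

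- p = 0.40: 0.767 (stated 0.77)
- p = 0.42: 0.797 (stated 0.80)
- p = 0.45: 0.836 (stated 0.84)

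The table reproduces. It rests on the two-or-more count, so it matches a limit of one DLT in six.

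**Step 2. What each limit allows.** The largest k with k/n within the limit is:

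| n | 17% | 33% literal | 33% as one third |
|---|---|---|---|
| 5 | 0 | 1 | 1 |
| 6 | 1 | 1 | 2 |
| 7 | 1 | 2 | 2 |
| 8 | 1 | 2 | 2 |

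At n = 6 the answer turns on 2/6 = 33.3%, which is just above a literal 33% but equal to one third. At n = 7 and n = 8 the limits differ on either reading.

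**Step 3. Size of the reading of 33% at n = 6.** These are binomial probabilities with all six patients treated, as in Table 7.6: 1.

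- True DLT rate 0.30: P(at most 1) = 0.42; P(at most 2) = 0.74.
- True DLT rate 0.42: P(at most 1) = 0.20; P(at most 2) = 0.50.

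At 0.42, the 80% chance of rejecting the dose quoted in protocol 7.6 would fall to 1 − 0.50 = 50% if two in six were acceptable.

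**Step 4. Effect of one replaced patient who was dosed.**

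| 3+3 count | Replaced patient | Treated Set | Within 17%? | Within 33%? |
|---|---|---|---|---|
| 1/6 = 16.7% | no DLT | 1/7 = 14.3% | yes | yes |
| 2/6 = 33.3% | no DLT | 2/7 = 28.6% | no | yes |
| 1/6 = 16.7% | DLT | 2/7 = 28.6% | no | yes |

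In the second row the protocol count stops the dose, while the Treated Set rate meets the SAP limit. In the third row, where the replaced patient's DLT is left out of the 3+3 count, the dose is accepted on 1/6 but the Treated Set rate exceeds the protocol's 17%.

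**Step 5. How often the two sets would differ.** The documents give no replacement rate, so r is assumed. The chance of at least one replacement before six evaluable patients is 1 − (1−r)^6: 0.26, 0.47 and 0.74 for r = 0.05, 0.10 and 0.20. For a cohort that stays at three, 1 − (1−r)^3 gives 0.14, 0.27 and 0.49. These are chances that the denominators differ, not that a decision changes.

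**The case against.** The strongest reply is that the protocol already states its counting basis. Protocol 7.3.1, the primary analysis section, ties the MTD to replacement and to a count out of six, apart from the general Treated Set sentence in 7.3. The visible SAP displays (7.7 and 7.7.1.1) are a count and a listing by dose group; no visible text plans a DLT percentage on the Treated Set. At exactly six patients a literal 33% gives the same answer as 17%. Text is redacted after SAP 6.3 and in 7.7.1.1, and the SAP follows three amendments that are not supplied, any of which may have changed the limit. On replaced patients, withdrawal due to DLT is already protected. The 5.2.1 sentence on inadequate treatment can be read as deciding whether an event is a DLT at all.

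Most of this stands, and it narrows the point. It does not explain the two limits: neither supplied document does so, and SAP section 4, where changes to the planned analysis are described, does not mention them. Nor does it supply a denominator for the incidence in SAP 5.1.

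A reader might infer three stronger things that the documents do not support:

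- **That the mismatch can reverse a dose decision.** The decision under protocol 4.1.6 is a count, and two DLTs stop the cohort whatever the denominator.
- **That the plan has no DLT population.** The relevant places are partly redacted, so absence cannot be asserted.
- **That patients in the expansion to 24 enter the MTD criterion.** Protocol 4.1.6 exempts that cohort from the two-DLT stop, 5.2.1 bases the MTD on the escalation cohorts, and no document states a test on 24 patients.

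**Conclusion.** The point holds as a conflict in the primary-endpoint criterion, made worse by an unsettled denominator, and should be fixed. On the supplied texts, 17% and 33% cannot both define the MTD. They agree only when the denominator is six and 33% is read literally. One replaced patient is enough to separate them (2/7 = 28.6%).

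What is affected is the stated criterion and the reported rate. The replaced-patient DLT is a narrow case, on which the wording of protocol 4.1.6 leans towards counting. The conclusion assumes that the redacted text and the amendments do not already settle these matters; confidence is medium for that reason. This review takes no position on which limit is right.

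**What to change.** 1. Reconcile protocol 5.2.1 and 7.3.1 with SAP 5.1 on the DLT limit. If an amendment changed it, cite that amendment in the SAP. State how 2/6 is read against the 33% limit.
2. In SAP 5.1, 6.3 and 7.7.1.1, report the first-course DLT numerator and denominator on the patients the 3+3 rule counted, with the Treated Set beside it as a check.
3. Reconcile protocol 4.1.6, 5.2.1 and 6.3.1 on whether a DLT in a replaced patient counts. Until that is done, list each such DLT and show the rate with and without it. Do not build the answer into the definition of the set.
4. Optionally, show escalation, expansion and QT-cohort patients at the same dose separately. Under SAP 3.2 some QT-cohort patients received a two-hour infusion in course 1.

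The cost is wording and one table. The reported DLT rate may look slightly less favourable than on the Treated Set, for example 2/6 in place of 2/7.

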6.5 POOLING OF CENTRES

There are only two centres in this trial. In general centres will be pooled. Due to the fact that a centre effect can not be excluded, specific analyses might be performed by centre additionally. Apart from that, centre effects will be described descriptively.

6.6 HANDLING OF MISSING DATA AND OUTLIERS

If not stated otherwise, missing data will not be imputed and remain missing.

[REDACTED].

Adverse Event

Missing or incomplete AE dates are imputed according to BI standards (

[REDACTED]

PK data

Missing data and outliers of PK data is handled according to

[REDACTED]

[REDACTED]

[REDACTED]

ECOG Performance Score

In case of non-available values of ECOG score at the time point before first administration the score measured just before administration on day 1 of first course will be considered as

baseline. In case the ECOG score was not determined at the end of treatment visit, the last ECOG score available will be used instead.

[REDACTED]

[REDACTED]

[REDACTED]

[REDACTED]

Date of progression (progdt)

If progression date (progdt) is missing for the evaluation of progression free survival, the corresponding visit date/examination date (visdt/examdt) is taken instead.

[REDACTED]

[REDACTED]

[REDACTED]

[REDACTED]

[REDACTED]

[REDACTED]

ECG

If one or two of the three consecutive ECG measurements is missing the available data will be used for that point in time.

Assessment of ECG for patients of the extension cohort for additional QT/QTc analysis:

If one baseline measurement is missing, this will be replaced by the other baseline measurement. If both baseline measurements are missing, this will be replaced by the measurement obtained at screening. Otherwise, baseline is missing and the patient is excluded for that endpoint.

Assessment of ECG for all other patients:

If one baseline measurement is missing, this will be replaced by the other baseline measurement. If both measurements are missing, the baseline is missing and the patient is excluded for that endpoint.

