### 5.2.3. Physical examination, height, body weight, performance status and electrocardiogram

A general physical examination will be performed at screening and at the end of the treatment. The same investigator should perform this examination. Physical examination will include measurement of height and of body weight and the evaluation of the ECOG performance score. Height will be documented only once at screening of course 1. Weight and ECOG score will also be assessed when BI 6727 treatment is started and at the end of the treatment. ECOG will also be assessed at the last visit of each course.

12-lead resting electrocardiograms (ECG) will be performed at baseline, at visit 2 before and at the end of BI 6727 infusion and at the last visit of each course. In patients eligible for repeated courses of treatment ECGs should be done at visit 2 of the third course (second repeated course) before and at the end of infusion of BI 6727, at the last visit of that course and whenever the investigator deems necessary. In case of drug related ECG changes additional ECG monitoring will be performed in the respective and later courses of treatment. Except for the screening ECG all ECGs have to be digitally recorded using dedicated equipment provided by a CRO [REDACTED]. ECG recordings will be done at the following time points:

- One ECG during the screening examination (no digital monitoring needed)
- On day 1 a series of three consecutive ECGs prior to start of infusion of BI 6727 (approx. experimental time -0:15 min)
- On day 1 a series of three consecutive ECGs after end of infusion of BI 6727 (approx. experimental time 1h 15 min)
- On day 1 of course 3 a series of three consecutive ECGs prior to start of infusion of BI 6727 (approx. experimental time -0:15 min)
- On day 1 of course 3 a series of three consecutive ECGs after end of infusion of BI 6727 (approx. experimental time 1h 15 min)
- At the visit 8 of the first course and visit 5 of the third course a series of three consecutive ECGs

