### 6.1 VISIT SCHEDULE

#### 6.1.1. Visit schedule in initial treatment course

##### 6.1.1.1. Visit 1 – screening visit

The screening visit has to be performed within day -14 and the day before first administration of BI 6727.

##### 6.1.1.2. Visit 2 – day 1

Visit 2 is the day of administration of BI 6727.

##### 6.1.1.3. Visit 3 – day 2

Visit 3 is the day after the first administration of BI 6727.

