## **6.2 TRIAL PROCEDURES AT EACH VISIT**

### **6.2.1 Screening phase**

Visit 1 – Screening visit (day -14 to day 0)

- informed consent
- demographics (sex, birth date, race)
- history (oncological and relevant non oncological)
- patient eligibility (in- and exclusion criteria)
- physical examination including resting ECG, body weight, height, vital signs (blood pressure, pulse rate) and ECOG performance score
- pregnancy test in women of childbearing potential
- concomitant therapy
- Endosonography or ultrasound of primary or metastatic marker lesions (optional)
- tumour assessment. MRI and CT scans should not be older than 4 weeks
- tumour markers (in applicable tumour types of the underlying disease)
- laboratory examination including safety lab parameters (haematology including differential, biochemistry, coagulation parameters), urine dipstick

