Note: For calculating the change in CTCAE grade from baseline/ pre-dose level, patients with a CTCAE grade of -9 will be reviewed on a case-by-case basis. If there is no suggestion that the corresponding laboratory value is of clinical significance, these values will be changed to -7 and treated as a CTCAE grade of 0 for analyses. All other values with CTCAE grade -9 will be regarded as CTCAE grade -8. Values with a CTCAE grade of -8 will either be removed from analyses concerning determination of baseline and worst CTCAE grade or if needed the category “not covered by CTC criteria” will be included. Values with CTCAE grades of -7 and -8 will be displayed in two separate listings.

In a similar manner, patients with a CTCAE grade of -1 will be reviewed on a case-by-case basis. For uric acid, values with CTCAE grade -1 will be regarded as either CTCAE grade 3 or CTCAE grade 1, depending on whether accompanied with physiological consequences or not.

The worst post baseline laboratory value and its CTCAE grade over all treatment courses will be calculated for each laboratory parameter specified above.

The time to worst CTCAE value [in days] will be defined as the time from first administration of trial medication to the first occurrence of the worst CTCAE grade. (Date of first occurrence of worst CTCAE grade – date of first administration of trial medication + 1).

The last value on treatment will be determined using a similar algorithm to the adverse events, and presented descriptively.

The change of the CTCAE grade of the lab value will be calculated

- from baseline to the last laboratory value on treatment
- from baseline to the worst value on treatment

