6.7 BASELINE, TIME WINDOWS AND CALCULATED VISITS

Study days and visits will be labelled according to the flow chart on page 6-8 of the CTP.

Unless otherwise specified, baseline is defined as the time-point closest to but prior to first administration of trial medication in the first treatment phase, where the first administration of trial medication is defined in [Section 6.3](#) above.

However, in the case of laboratory data, if the time is missing but the date of lab assessment is equal to the first medication date, [REDACTED]

[REDACTED]. This will then become the baseline value.

ECG

Baseline ECG is available from two courses. To account for possible variations between the study days, two different baseline definitions will be used:

1. Individual baseline is defined as the mean of the triplicate at the time-point closest to but prior to the start of the infusion of each treatment course, i.e. each treatment course has its own baseline.
2. Combined baseline is defined as the mean of the (two) triplicates at the time-point closest to but prior to the start of the infusion of both treatment courses, i.e. a common baseline is used for both treatment courses.

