7.7.2 Laboratory data

The analyses of laboratory data will be descriptive in nature and will follow the standard procedure laid down in the [DM & SM](#) (Guideline 'Display and Analysis of Laboratory Data').

Patients will be counted under the initial treatment. Separate listings for patients treated under different doses will be created. The analysis of laboratory data will use the same ‘analysing treatments’ as described for the AEs.

Single time courses by initial treatment will be used to display laboratory values over time. The graphs may be truncated if sufficient data is not available. These graphs will be displayed in Chapter 16.1.9.2 for the following parameters, using the BI normalised values for Haematology and Differentials, and the multiples of the ULN for Substrates and Enzymes:

Haematology: Haemoglobin, WBC count and Platelets

Differentials: Neutrophils (absolute count)

Substrate: Creatinine, Total Bilirubin and Creatinine Phosphokinase

Enzymes: AST, ALT and γ -Glutamyl transpeptidase (GGT)

In addition, laboratory tests will be analysed within the treatment courses as defined below. Maximum CTCAE grades will be tabulated by treatment course and over the entire trial.

Where applicable, standard CTCAE grading Shift tables from first visit to end of trial will be generated in Appendix 16.1.9.2.

Number of patients treated [N (%)]

Number of patients with maximum change of CTCAE grade [N (%)]

Number of patients with transition of CTCAE grade:

- from baseline to the last value on treatment [N (%)]
- from baseline to the worst grade on treatment [N (%)]
- from worst to the last value on treatment [N (%)]

Clinically relevant abnormalities [REDACTED] will also be summarised.

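### SAP 6.6 in effect makes the screening ECOG score the baseline and the day 1 pre-dose score only a fallback, so ECOG change before any drug is given enters the change-from-baseline tables

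*SAP*

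**What the plan says.** **Schedule.** The protocol places two ECOG assessments before drug. Protocol 6.2.1 lists at screening "physical examination including resting ECG, body weight, height, vital signs (blood pressure, pulse rate) and ECOG performance score". Protocol 5.2.3 adds: "Weight and ECOG score will also be assessed when BI 6727 treatment is started and at the end of the treatment". The flow chart for the initial course and Protocol 6.2.2.1 (visit 2) agree. Protocol 6.1.1.1 sets the gap: "The screening visit has to be performed within day -14 and the day before first administration of BI 6727".

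**Default baseline.** SAP 6.7: "Unless otherwise specified, baseline is defined as the time-point closest to but prior to first administration of trial medication in the first treatment phase".

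**ECOG rule.** SAP 6.6, under missing data: "In case of non-available values of ECOG score at the time point before first administration the score measured just before administration on day 1" of the first course is taken as baseline.

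**Use.** SAP 5.2.3 computes end-of-treatment score minus baseline score and sorts it into improved, unchanged or deteriorated at a threshold of one point. It does not define the baseline. SAP 7.5 tabulates both the change and the three-level scale.

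**The concern.** The score closest to dosing is the natural reference for change on treatment, and SAP 6.7 adopts that principle. The ECOG sentence in SAP 6.6 turns the order round without giving a reason, inside a rule for missing values where a reader would not look for a baseline definition.

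What is at stake is how the ECOG tables are read. Patient performance is part of the first secondary endpoint in Protocol 2.3, and ECOG change is a secondary endpoint in SAP 5.2.3. One point is enough to change a patient's category, and there is no control group in which drift before treatment would show. With the older score as baseline, a change that happened before any BI 6727 was given is indistinguishable in the table from one that happened afterwards. SAP 7.1.3 also summarises ECOG at baseline by initial treatment, so that table depends on the same choice.

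**Working it through.** The plan states no figure on this point, so there is none to reproduce. The check is a reading of the rules, then an enumeration, then an illustration of size.

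**1. Which score does SAP 6.6 make primary?** Only two ECOG scores are scheduled before drug: screening (visit 1) and day 1 (visit 2). SAP 6.6 names the day 1 score as the substitute.
- If the value being replaced were also the day 1 score, the rule would replace a missing value with itself.
- The only other scheduled score is screening. Screening is therefore primary and day 1 the fallback.

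**2. Comparison with the other baseline rules.**

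| Rule | First choice | Fallback |
|---|---|---|
| SAP 6.7 default | last time point before first dose (for ECOG, day 1) | next earlier value (implied) |
| SAP 6.6, ECG, extension cohort | pre-infusion ECGs | screening, if both are missing |
| SAP 6.6, ECOG | screening (inferred) | day 1 pre-dose |

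The ECOG row runs opposite to the other two.

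**3. Which patients change category?** Inputs: screening and day 1 scores of 0 to 2 (inclusion criterion 4, with eligibility checked again at visit 2), end-of-treatment scores of 0 to 5 and the one-point rule (SAP 5.2.3). There are 3 × 3 × 6 = 54 paths, and 14 are classified differently under the two baselines.

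| Shift before dosing | Screening baseline | Day 1 baseline | Paths (screening-day 1-end) |
|---|---|---|---|
| Decline | deteriorated | unchanged | 0-1-1, 0-2-2, 1-2-2 |
| Decline | deteriorated | improved | 0-2-1 |
| Decline | unchanged | improved | 0-1-0, 0-2-0, 1-2-1 |
| Improvement | improved | unchanged | 1-0-0, 2-0-0, 2-1-1 |
| Improvement | improved | deteriorated | 2-0-1 |
| Improvement | unchanged | deteriorated | 1-0-1, 2-0-2, 2-1-2 |

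Seven paths involve decline before dosing and seven are their mirror image. These are counts of paths, not patient frequencies.

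**4. Size, under assumptions.** The documents give no rate of ECOG change between screening and day 1. Suppose a fraction q declines by one point in that window and is stable afterwards. The number tabulated as deteriorated with no change after dosing is n × q:
- n = 24 (at the MTD): q = 5%, 10%, 20% gives 1.2, 2.4, 4.8.
- n = 80 (planned maximum): 4, 8, 16.

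**5. Direction.** Let d decline and i improve by one point before dosing, independently of an assumed on-treatment split of 30% worse, 60% same, 10% better. With the screening baseline:
- Deteriorated = 0.9d + 0.3(1 − d − i), so it moves from 30% by 0.6d − 0.3i.
- Improved = 0.7i + 0.1(1 − d − i), so it moves from 10% by 0.6i − 0.1d.
- Patients whose category changes = 0.7d + 0.9i.

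With d = 10%, i = 2.5%: deteriorated 0.09 + 0.2625 = 35.3%; improved 0.0175 + 0.0875 = 10.5%; category changed 0.07 + 0.0225 = 9.3%.

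With d = i = 10%: deteriorated 0.09 + 0.24 = 33%; improved 0.07 + 0.08 = 15%; category changed 0.07 + 0.09 = 16%.

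The direction of the distortion therefore depends on the ratio of decline to improvement, which the documents do not give. This sketch also ignores the ECOG limit of 2 at entry.

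**The case against.** **It is not a contradiction.** SAP 6.7 gives way where something else is specified, and a rule specific to ECOG is just such a specification. This stands. A reader might infer that 6.6 and 6.7 conflict outright; they do not. What remains is an exception that is unexplained and has to be inferred.

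**The two rules may even agree.** SAP 6.3 defines first administration by date, and SAP 6.7 has a special, partly redacted clause for laboratory values dated on the first medication day with no time. Read by date, a day 1 ECOG score is not clearly before dosing, and SAP 6.6 would simply admit it when nothing earlier exists. This reading is possible, but screening is still the operative baseline under it, so the practical consequence is the same.

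**SAP 6.6 never mentions screening.** True. The reading is an inference, though the only one in the protocol's schedule that gives the sentence a function.

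**The laboratory shift tables.** A reader might extend the point to SAP 7.7.2, where "standard CTCAE grading Shift tables from first visit to end of trial will be generated". The documents do not support that. The same section lists transitions from baseline to the last value and to the worst grade on treatment, matching SAP 5.2.5 ("from baseline to the last laboratory value on treatment"). Nor need first visit mean screening: SAP 5.2.3 uses the term for the first visit of each course.

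**Small consequence.** SAP 3.3 makes all analyses descriptive, and the SAP does not attribute ECOG change to the drug. Both points stand and limit the weight of the issue.

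**Conclusion.** The point holds in a limited form. SAP 6.6 in effect uses the older of two available pre-treatment ECOG scores as baseline, by up to about 14 days, and SAP 5.2.3 leaves the baseline unnamed. A shift before dosing is then carried into the end-of-treatment change and can move a patient between the three categories.

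A reader might infer that the rule systematically inflates deterioration on BI 6727. The documents do not support this: the effect runs both ways, and a net excess of deterioration needs an assumed preponderance of decline before dosing. The illustrated sizes (about 1 to 5 of 24, or 4 to 16 of 80, for a 5% to 20% one-point decline followed by stability) rest wholly on that assumed rate; 80 is also a ceiling on enrolment. The effect is confined to the descriptive ECOG tables, and the DLT counts and the MTD are unaffected.

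**What to change.** In SAP 5.2.3, define baseline ECOG as the score at visit 2 (day 1 of course 1) before infusion. In SAP 6.6, reverse the order so that the screening score is used only if the day 1 score is missing. The protocol sets no clock time for the day 1 score, so the derivation should go by visit rather than by time stamp. If the sponsor prefers screening as baseline, SAP 5.2.3 should say so and give the reason.

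The cost is two sentences and one changed derivation, which also feeds the baseline ECOG summary in SAP 7.1.3. Both scores are already scheduled, so no new data are needed. SAP 7.7.2 needs no change on this account.

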5.2.3 Eastern Cooperative Oncology Group (ECOG) Performance Score

ECOG score: The scale of ECOG score is defined as a six point categorical scale as described in ([R01-0787](#)) ranging from 0 (asymptomatic) to 5 (death). Calculation was to be carried out for each patient, for each first visit of each treatment course, each last visit of each treatment course, the end of treatment and the follow up visit.

ECOG score change from baseline to end of treatment will be calculated, and defined as

= ECOG score at end of treatment – ECOG score at baseline.

Scale of ECOG score change: The ECOG score changes from baseline score will be categorized on a three point categorical scale: deteriorated, unchanged, and improved. Improvement or deterioration of performance status will require a decrease or an increase from baseline, respectively, of at least one point on the ECOG scale.

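### SAP 6.6 lets a pre-dose ECOG score stand in for a missing end-of-treatment score, so a treated patient with no post-dose ECOG still gets a change category, usually *unchanged*

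*SAP*

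**What the plan says.** The general rule in SAP 6.6 is "If not stated otherwise, missing data will not be imputed and remain missing". ECOG is a stated exception: "In case the ECOG score was not determined at the end of treatment visit, the last ECOG score available will be used instead". The visible text does not limit this to scores taken after dosing, and it gives no rule for patients who have died.

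SAP 5.2.3 uses a six-point scale from 0 to 5, where 5 is death. It states that "ECOG score change from baseline to end of treatment will be calculated", as the end-of-treatment score minus the baseline score. The result is "categorized on a three point categorical scale: deteriorated, unchanged, and improved", and a move in either direction needs a shift "of at least one point on the ECOG scale". Besides the first visit of each course, SAP 5.2.3 lists ECOG at "each last visit of each treatment course, the end of treatment and the follow up visit". Protocol 5.2.3 agrees on the course schedule: "ECOG will also be assessed at the last visit of each course".

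Patient performance is part of the first secondary endpoint (Protocol 2.3). SAP 7.5 plans tables of both the score change and the three-category scale. The analysis set is everyone dosed at least once (SAP 6.3).

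**The concern.** The end-of-treatment change is meant to show how patients fared after receiving the drug. If the substituted score can be a pre-dose score, some patients enter the table with a result that contains nothing observed after treatment. They would include patients who died or disappeared within the first three weeks, which is not a neutral outcome. Placing them in the middle category makes the table look better than the data behind it.

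The rule itself creates the problem. Under the SAP's own default these patients would simply be missing. The SAP also allows for such cases: its exposure-time definition in 5.3.3 provides for death less than 21 days after the last administration.

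**Working it through.** The documents give no rate of missing ECOG scores and no expected ECOG change, so there is no figure to reproduce. The check applies the SAP's rule to each possible score history.

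**Inputs**

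- Change = end-of-treatment score − baseline. At least +1 is *deteriorated*, at least −1 is *improved*, 0 is *unchanged* (SAP 5.2.3).
- Baseline = the value closest to, but before, the first dose (SAP 6.7). In course 1 that is normally the day 1 pre-dose score.
- ECOG in course 1: screening, day 1 pre-dose, day 22 (±2) and end of treatment (Protocol initial-course flow chart, 5.2.3 and 6.2.2.1).
- Follow-up visits cover only patients who completed a course, including the day 22 visit (Protocol 6.2.3). They supply no score for someone lost before day 22.
- Patients replaced under Protocol 6.3.1 have been dosed and stay in the Treated Set (SAP 6.3).
- Eligible baseline scores are 0 to 2 (Protocol 3.3.1).

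**Applying the rule**

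| Patient | Baseline | Score used | Change | Category |
|---|---|---|---|---|
| Dies on day 10, only pre-dose scores, SAP 6.7 baseline | 1 | 1 (day 1) | 0 | unchanged |
| Same patient, death entered as 5 | 1 | 5 | +4 | deteriorated |
| Same patient, screening baseline 1, day 1 score 2 | 1 | 2 (day 1) | +1 | deteriorated |
| Drops out in course 2, day 22 score 2 | 1 | 2 (day 22) | +1 | deteriorated |
| Drops out in course 2, day 22 score 0 | 1 | 0 (day 22) | −1 | improved |

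The first row is the automatic zero: baseline − baseline = 0. The third row is not zero, but it compares two scores taken before any drug was given. The last two rows use real post-dose scores and can fall in any category.

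If death is scored as 5, eligible baselines of 0, 1 and 2 give +5, +4 and +3, always *deteriorated*.

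**Size per patient**

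Moving one early death from *unchanged* to *deteriorated* shifts the deteriorated share by 1/n:

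- cohort of 3: 1/3 = 33 percentage points
- cohort of 6: 1/6 = 17 points
- 24 patients at the MTD: 1/24 = 4 points
- all 80 patients pooled: 1/80 = 1.25 points

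**Illustration (assumed rates)**

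Suppose a fraction f of 80 patients has no post-dose ECOG, and 30% of the others deteriorate. The rule reports (1 − f) × 30%. The upper bound, with every such patient counted as deteriorated, is (1 − f) × 30% + f.

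| f | Patients | Reported | Upper bound |
|---|---|---|---|
| 5% | 4 | 28.5% | 33.5% |
| 10% | 8 | 27% | 37% |
| 20% | 16 | 24% | 44% |

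Neither f nor the 30% is in the documents.

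**The case against.** A reader might infer that everyone who dies or drops out before end of treatment is tabulated as *unchanged*. The documents do not support that. Protocol 6.2.3 asks for the end-of-trial investigations, which include ECOG, at the last visit of patients who withdraw or drop out; where that is done the rule is not needed. Anyone who reaches day 22 normally has a post-dose score. In later courses the carried score may be out of date, but it was taken after the first dose and can fall in any category. The repeated-course flow chart leaves ECOG out at visit 5 while Protocol 5.2.3 and 6.2.2.2 require it. That is a separate scheduling inconsistency and does not widen this point.

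The zero is not certain even for early losses. The ECOG sentence just before the carry-forward rule in SAP 6.6 uses the day 1 score as baseline only when an earlier pre-dose value is unavailable, which suggests a screening baseline. SAP 6.7 applies only where nothing else is specified. This objection stands against a guaranteed *unchanged*. It does not help the rule, because the result still contains no post-dose observation.

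A death might also be entered as ECOG 5 in practice, since the scale provides for it, and blacked-out lines that follow the ECOG rule could bear on this. The visible text makes no such link, and the sponsor can check this at once.

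A reader might further infer that the distortion grows with dose. Nothing in the documents shows this: toxicity withdrawals should have an end-of-treatment ECOG, and patients with DLT may be eligible for further courses.

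Finally, the table is descriptive (SAP 3.3), and early failures appear elsewhere: death can count as a PFS event (SAP 5.2.2), discontinuations are listed with reasons (SAP 7.1.1), and serious adverse events are tabulated (SAP 7.7.1.2). That stands, and it limits the severity.

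**Conclusion.** The point holds in a narrow form and is minor. It concerns treated patients with no ECOG score after the first dose: essentially those who die or are lost before day 22 of course 1, have no end-of-treatment assessment, and have no ECOG 5 entered for a death. For them SAP 6.6 substitutes a pre-dose score. With the SAP 6.7 baseline the outcome is *unchanged*; with a screening baseline it is a comparison of two pre-dose scores.

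Deterioration can be understated by about 17 percentage points for each such early death in a cohort of six, assuming the SAP 6.7 baseline and a table split by starting dose. SAP 7.5 states that split for the tumour-response tables but does not repeat it for ECOG. The overall effect cannot be sized, because the number of such patients is not given. MTD, DLT and PFS do not use this rule and are unaffected.

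**What to change.** In SAP 6.6:

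1. Carry forward only ECOG scores recorded after the first administration of BI 6727.
2. Count a death before the end-of-treatment score as ECOG 5, and so as *deteriorated*, using the scale already in SAP 5.2.3.
3. Show other patients without a post-dose score in a separate row, *no post-baseline value*.
4. Reconcile the ECOG baseline sentence in 6.6 with 6.7, so that it is clear whether the screening or the day 1 score is the baseline.

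The cost is a few sentences and a small program change. The ECOG table will look slightly less favourable. The second item also applies to deaths in later courses that precede an end-of-treatment score, so a footnote giving the number of patients scored 5 because of death would keep decline in performance distinct from mortality.
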